3.6. Dose Administration

Participants who tolerate their optimized dose in the Lixivaptan Titration Period will then enter the Double-blind, Randomized Treatment Period during which time they will take the lixivaptan dose level achieved at the end of the Lixivaptan Titration Period if participants were randomized into the lixivaptan group or receive matching placebo capsules if participants were randomized into the placebo group. During the Double-blind, Randomized Treatment Period, the dose may be adjusted downward at the Investigator's discretion if needed to manage non-hepatic side effects. For these participants, the dose level should be increased back to the dose at the start of the Double-Blind, Randomized Treatment Period, once symptoms resolve. The Investigator may temporarily interrupt the study drug, if necessary, to manage acute intercurrent illness, tolerability issues, planned or unplanned surgical procedures or life situations, e.g., airplane travel, etc. In an effort to minimize missing data, wherever practicable, participants who experience a study drug interruption of 7 or more days will be scheduled to have 3 separate serum creatinine samples obtained (minimally 24 hrs. apart between 8 and 28 days after their last dose) for determination of eGFR. Participants who require a prolonged interruption (i.e., >4 weeks in duration) due to illness, including COVID-19, or other reasons may be able to restart the study drug when medically stable. Re-establishment is required in the event of a prolonged interruption. If study drug is interrupted for longer than 8 weeks, then study drug treatment will be permanently discontinued. Note: In the event of tolerability issues at any time during the study, dosing may be decreased or temporarily stopped. If dosing is resumed during the Double-Blind, Randomized Treatment Period at a dose level less than that achieved at Visit 9, attempts will be made every 4 to 8 weeks to re-establish the previously achieved dose level from Visit 9, if medically appropriate.

For the participants who completed Part 1 and continued to Part 2, the lixivaptan re-titration is required. During the Lixivaptan Re-titration Period, dosing will start at Level 1 (50 mg BID) for all participants in Part 2 and will be increased weekly until the dose level taken at the end of the Double-blind, Randomized Treatment Period is achieved, or, if they had received placebo during the Double-blind, Randomized Treatment Period, to the last inferred dose level (the dose level

equal to the active dose level had the participant been randomized to the active arm). Re-titration will be performed by the IRT, and the site, participant, and sponsor maintain a blinded status to the prior treatment assignment in Part 1. The dose level obtained at end of the Lixivaptan Re-Titration Period and equivalent to the dose level taken at the end of Double-blind, Randomized Treatment Period, will be continued for the remainder of Part 2. In the event of tolerability issues at any time during the study including either during the Lixivaptan Re-titration Period or during the Maintenance Treatment Period, dosing may be decreased or temporarily stopped. Attempts will be made every 4 to 8 weeks to re-establish the previously achieved dose level at the end of the Double-blind, Randomized Treatment Period of Part 1, if medically appropriate. If tolerability continues to be problematic, the participant may continue at the lower dose. If study drug is interrupted for longer than 8 weeks, then study drug treatment will be permanently discontinued.

3.7. Sample Size

Part 1:

Based on the results of the REPRISE trial with tolvaptan (Torres et al, 2017), it is assumed that the standard deviation for the primary efficacy endpoint, change from baseline to post-treatment follow-up in mean eGFR, is 6.20 mL per minute per 1.73 m². Assuming a between-treatment group difference of -1.40 mL per minute per 1.73 m² and a randomization ratio of 2:1 for lixivaptan to placebo, a sample size estimate of 1314 participants (438 placebo-treated participants and 876 lixivaptan-treated participants) is required to achieve 90% power at a significance level of 0.01. This estimate has been adjusted up to 1350 participants (450 placebo participants and 900 lixivaptan participants). It is estimated that approximately 2250 participants will need to be screened in order to randomize 1350 participants.

Part 2:

This is a convenience sample based on the number of participants who elect to continue into Part 2. It is estimated that approximately 1350 participants will be randomized in Part 1. All participants except those who discontinue due to an adverse event or withdraw consent will continue into Part 2. Approximately 90% (1215) of Part 1 participants are anticipated to continue into Part 2.

3.8. Schedule of Events

Please see the protocol for a detailed schedule of events.

4. Study Endpoints

4.1.1.2. Secondary Efficacy Endpoints

The secondary endpoints are:

- The annualized rate of change (slope) in eGFR, estimated from all on-treatment eGFRs, calculated from the CKD-EPI equation (2021 CKD-EPIcr_R) for serum creatinine, during the Double-Blind, Randomized Treatment Period in Part 1. An on-treatment eGFR is defined as any eGFR obtained while participants are on treatment (taking the study drug), i.e., any eGFR obtained within 24 hours after the latest dose.
- The annualized percent change in height-adjusted TKV (htTKV, mL/m) from baseline to post-treatment follow up during Follow-up Period I after Week 52 for on-treatment completers, or, for participants who discontinue study drug treatment prior to Week 52 [Visit 22], during the Follow-up Period 28 days following study drug treatment discontinuation. The htTKV is defined as the TKV value (mL) determined by MRI divided by the participant's baseline height (meters) measured at Screening. Baseline htTKV is the one obtained at Screening (Visit 1a).

4.1.1.3. Exploratory Efficacy Endpoints

• The annualized percent change in height-adjusted LV (htLV, mL/m) from baseline to post-treatment follow up during Follow-up Period I after Week 52 for on-treatment completers, or, for participants who discontinue study drug treatment prior to Week 52 [Visit 22], during the Follow-up Period 28 days following study drug treatment discontinuation. The htLV is defined as the LV value (mL) determined by MRI divided

by the baseline participant's height (meters) observed at Screening. Baseline htLV is the one obtained at Screening (Visit 1a).

- Mean change from baseline in morning spot urine osmolality at Visits 15, 22, and 25; Baseline is defined as urine osmolality obtained at Screening (Visit 2).
- The annualized change in eGFR calculated from the 2021 CKD-EPIcr-cys_R equation from baseline to the post-treatment follow-up. The definitions of baseline eGFR, post-treatment follow-up eGFR, elapsed duration, and annualization are the same as the primary efficacy endpoint except for using the different eGFR equations.

4.1.2. Health Outcome Endpoints

4.1.2.1. Medical Resource Utilization Endpoints

A detailed description of the analysis for the medical resource utilization and health economics assessments will be specified in a prospective health outcomes analysis plan.

4.1.2.2. Patient Reported Health Outcomes

Endpoints for Patient Reported Health Outcomes consist of three patient questionnaires: ADPKD-IS, ADPKD-PDS, and ADPKD-UIS. Number of questions, domains and scoring for each questionnaire are listed in Table 2. Baseline score in each domain is defined as the observed score for that domain at Screening (Visit 2). If more than 50% of the items of a domain are missing, that domain score is missing; otherwise, the domain score is the mean of scores for all the non-missing items for that domain.

HRQoL PRO	Description	Scoring		
ADPKD-Impact Scale (ADPKD-IS)	 18-item participant administered questionnaire Scale of 1-5 with a two week recall period; 1 = not difficult at all/not bothered at all to 5 = extremely difficult/extremely bothered 3 conceptual domains: physical, emotion and fatigue 	 Physical domain score = Items (1 + 2 + 3 + 4 + 5 + 15 + 16) /7 Emotional domain score = Items (6 + 11 + 12 + 13)/4 Fatigue domain score = Items (10 + 17 + 18)/3 Items 7, 8, 9, and 14 are not included in the scoring 		
ADPKD-Pain and Discomfort Scale (ADPKD-PDS)	 20-item participant administered questionnaire Scale of 1-5 with a one week recall period; 1 (none 	 Dull pain severity score = Items (1 + 2 + 3)/3 Sharp pain severity score = Items (4 + 5+ 6)/3 		

Table (2:	Domains	and th	eir Sc	oring	of Three	Patient	Reported	Health	Outcomes
I abit		Domains	and th		vi me	or runce	1 attent	reporteu	incantin	Outcomes

	or not at all) to 5 (extreme, constantly, or completely)	• Discomfort severity score = Items (7 + 8 + 9)/3
	• Severity dimension consists of 4 severity scales: dull pain severity, sharp pain severity, discomfort	• Overall pain severity score = (dull pain severity score + sharp pain severity score + discomfort severity score)/3
	severity, overall pain severityInterference dimension	• Dull pain interference score = Items (10 + 11 + 12 + 13 + 14)/5
	consists of 2 scales: dull pain interference, discomfort interference	• Discomfort interference score = Items (16 + 17 + 18 + 19 + 20)/5
		• Sharp pain interference score = Item 15
ADPKD-Urinary Impact Scale	• 11-item participant administered questionnaire	• Frequency domain score = Items $(1 + 3 + 6 + 8)/4$
(ADPKD-UIS)	• Scale of 1-5 with a one week recall period; 1 (not difficult/bothered) to 5 (very difficult/bothered)	• Urgency domain score = Items (2 + 4 + 7 + 9)/4
		• Nocturia domain score = Items $(5 + 10 + 11)/3$
	• 3 domains: frequency, urgency, and nocturia	

Endpoints for Patient Reported Health Outcomes at Visits 12, 15, 18, 22, and 25 are as follows:

ADPKD-IS:

- Change from baseline in physical domain score
- Change from baseline in emotional domain score
- Change from baseline in fatigue domain score

ADPKD-PDS:

- Change from baseline in dull pain severity score
- Change from baseline in sharp pain severity score
- Change from baseline in discomfort severity score
- Change from baseline in overall pain severity score
- Change from baseline in dull pain interference score
- Change from baseline in discomfort interference score
- Change from baseline in sharp pain interference score

ADPKD-UIS:

- Change from baseline in frequency domain score
- Change from baseline in urgency domain score
- Change from baseline in nocturia domain score

In addition, the above endpoints will be calculated at the evaluation visits during Lixivaptan Titration Period. Those will be analyzed separately.

4.1.3. Pharmacokinetic Endpoints

The calculation of parameters for population PK analysis of plasma lixivaptan concentrations will be described in a separate PK analysis plan.

4.1.4. Safety Endpoints

4.1.4.1. Key Safety Endpoint

The key liver safety endpoint is the incidence of participants with serum ALT levels $>3 \times ULN$ during the Double-Blind, Randomized Treatment Period in Part 1.

4.1.4.2. Secondary Safety Endpoints

The safety and tolerability of lixivaptan assessed through evaluation of:

- Treatment-emergent adverse events (TEAEs); a TEAE is defined as any adverse event that either occurred after the first dose of the study drug (i.e., placebo during the Placebo Run-in Period) or occurred prior to the first dose of the study drug but worsened after the first dose of the study drug.
- Clinical laboratory findings (clinical chemistry including additional analyses of liver chemistry, hematology, and urinalysis);
- Vital signs;
- 12-lead electrocardiograms (ECG).

4.2. Study Endpoints of the Open-label Phase (Part 2/Year 2)

4.2.1. Key Endpoints

4.2.1.1. Key Comparison Endpoint

The primary endpoint of Part 2 is the annualized change in eGFR calculated from the CKD-EPI equation (2021 CKD-EPIcr_R) for serum creatinine from baseline to the post-treatment follow-up in Part 2, annualized by participant's treatment elapsed duration in Part 2 as defined below. Baseline eGFR in Part 2 is defined as the mean of the 3 eGFR determinations obtained at 3 post-treatment follow-up visits (Visits 23, 24, and 25) after Week 52 in Part 1. The post-treatment follow-up eGFR of Part 2 is defined as the mean of 3 eGFR assessments obtained during the

Follow-up Period II after Week 104 for on-treatment completers or, for participants who discontinue study drug treatment prior to Week 104 [Visit 42], during the Follow-up Period 8 to 28 days following study drug treatment discontinuation in Part 2. The participant's treatment elapsed duration in Part 2 is defined as the number of years (number of days divided by 365.25) from the median of the collection dates of the baseline eGFR assessments to the median of the collection dates of the 3 eGFR assessments obtained during the post-treatment follow-up.

4.2.1.2. Key Safety Endpoint

The key liver safety endpoint is incidence of serum ALT levels $> 3 \times ULN$ in participants exposed to lixivaptan in Part 2.

4.2.2. Other Endpoints

4.2.2.1. Other Comparison Endpoints

The additional secondary endpoints are:

- The annualized rate of change (slope) in eGFR, estimated from all on-treatment eGFRs, calculated from the CKD-EPI equation (2021 CKD-EPIcr_R) for serum creatinine during the Maintenance Treatment Period in Part 2. An on-treatment eGFR is defined as any eGFR obtained while participants are on treatment (taking lixivaptan) in Part 2.
- The annualized percent change in htTKV from baseline (post-treatment follow-up after Week 52 in Part 1) to post-treatment follow-up during Follow-up Period II after Week 104 for on-treatment completers, or, for participants who discontinue study drug treatment prior to Week 104 [Visit 42], during the Follow-up Period 28 days following study drug treatment discontinuation in Part 2.

4.2.2.2. Secondary Safety Endpoints

The safety and tolerability of lixivaptan assessed through evaluation of:

- Treatment-emergent adverse events (TEAEs);
- Clinical laboratory findings (clinical chemistry including additional analyses of liver chemistry tests), hematology, and urinalysis);
- Vital signs;
- 12-lead electrocardiograms (ECG).

4.2.2.3. Medical Resource Utilization Endpoints

A detailed description of the analysis for the medical resource utilization and health economics assessments will be specified in a prospective health outcomes analysis plan.

4.2.2.4. Endpoints for Patient Reported Health Outcomes

See Section 4.1.2.2 for the definitions for domains, how to calculate domain scores, and the definitions of endpoints for each patient report health outcome questionnaire. Baseline in Part 2 is defined as the observed domain score in the post-treatment follow-up visit (Visit 25) after Week 52 in Part 1.

4.2.3. Pharmacokinetic Endpoints

The calculation of parameters for population PK analysis of plasma lixivaptan concentrations will be described in a separate PK analysis plan.

4.2.3.1. Exploratory Endpoints

- The annualized percent change in htLV determined by MRI from baseline (posttreatment follow-up visit [Visit 25] after Week 52 in Part 1) to post-treatment follow-up during Follow-up Period II after Week 104 for on-treatment completers, or, for participants who discontinue study drug treatment prior to Week 104 [Visit 42], during the Follow-up Period 28 days following study drug treatment discontinuation in Part 2;
- Mean change from baseline in morning spot urine osmolality in Part 2; Baseline is defined as urine osmolality obtained at 28 days post-treatment follow-up visit (Visit 25) after Week 52 in Part 1.
- The annualized change in eGFR calculated from the 2021 CKD-EPIcr-cys_R equation from baseline to the post-treatment follow-up. The definitions of baseline eGFR, post-treatment follow-up eGFR and annualization are the same as the key comparison endpoint in Part 2 (Section 4.2.1.1) except for using the different eGFR equations.

5. Analysis Populations

The following analysis populations are planned for this study:

Part 1:

- **Placebo Run-in Safety Set:** The Placebo Run-in Safety Set includes all participants who received at least one dose of placebo during Placebo Run-In Period in Part 1.
- Lixivaptan Titration Safety Set: The Lixivaptan Titration Safety Set includes all participants who received at least one dose of lixivaptan during Lixivaptan Titration Period in Part 1.
- **Randomized Safety Set:** The Randomized Safety Set includes all participants who received at least one dose of study drug after randomization.
- Intent-to-Treat Analysis Set (ITT): The ITT includes all participants who were randomized in Part 1.

- **Modified Intent-to-Treat Analysis Set (mITT):** The mITT includes all participants in the ITT who received at least one dose of study drug in Part 1. Note that the mITT Analysis Set consists of the same set of the participants in the Randomized Safety Set.
- **Primary Efficacy Analysis Set (PEAS):** The PEAS includes all participants in the mITT Analysis Set who have both baseline and at least one assessment of eGFR after the treatment is complete or discontinued in Part 1.
- Secondary Efficacy Analysis Set (SEAS): The SEAS includes all participants in the mITT Analysis Set who have both baseline and at least one on-treatment assessment of eGFR.
- **Per-protocol Efficacy Analysis Set (PPAS):** The PPAS includes all participants in the PEAS who do not have any protocol deviations that are deemed to potentially impact efficacy.

Assignment of participants to populations will be confirmed at a blinded data review meeting to be held before the study database is locked for Part 1.

Part 2:

- **Part 2 Safety Set (P2SS):** The Part 2 Safety Set includes all participants who receive at least one dose of lixivaptan in Part 2.
- **Part 2 Efficacy Analysis Set (P2EAS):** The Part 2 Efficacy Analysis Set includes all participants in the Part 2 Safety Set who have at least one assessment of off-treatment eGFR in Part 2.

Parts 1 & 2 (Combined):

• Lixivaptan Treated Safety Set (LTSS): The Lixivaptan Treated Safety Set is defined as all participants who received at least one dose of lixivaptan treatment after randomization during the entire study. This analysis population will be used to summarize safety data during the study for all randomized, lixivaptan-treated participants.

6. General Issues for Statistical Analysis

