8.4.2 Sensitivity Analysis of the Primary Efficacy Analysis

In particular, in order to address the impact of missing data on the results from the primary efficacy analysis, a number of sensitivity analyses will be performed. The detailed sensitivity analyses for the primary efficacy analysis will be described in the statistical analysis plan (SAP).

Amongst these sensitivity analyses, the main sensitivity analysis of the primary efficacy analysis will use the mean of eGFR values obtained pretreatment and the mean of eGFR values obtained off treatment after the end of the 52-week treatment period, regardless of adherence to randomized treatment and/or withdrawal for all randomized participants, i.e., Intent-To-Treat participants. Missing values at Week 52 will be imputed using multiple imputations (assuming missing at random). Tipping point analyses will be included using a pattern-mixture model to impute missing data at Week 52 (assuming missing not at random) by systematically varying assumptions about the missing outcomes on the two treatment arms – these tipping point analyses will be bi-dimensional, i.e., allow the assumptions about the missing outcomes in the two arms to vary independently, and will include scenarios where the dropouts on the lixivaptan arm have worst outcome compared to placebo dropouts.

8.5 Secondary Efficacy Analyses.

If the primary efficacy analysis is statistically significant at the 1% level of significance, then the secondary efficacy endpoints of (1) annualized rate of change (slope) in eGFR based on all on-treatment eGFR determinations during the Double-blind, Randomized Treatment Period calculated from the CKD-EPI_{cr}_R equation for serum creatinine; and (2) annualized change in TKV as measured by MRI will be analyzed. Each will be tested at the 1% level of significance in sequential order using a closed testing procedure on the SEAS. The details of the testing procedure will be provided in the SAP for the study.

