8.1. Definition of Completer and Non-completer

Part 1 completer and non-completer will be defined as the following:

- On-treatment completer: all the randomized participants who take double-blind study drug in accordance with the protocol through Visit 22 (Week 52), and complete some or all of their required trial visits/assessments through Visit 22 and have at least one follow-up serum creatinine assessment during off-treatment Follow-up Period I.
- Off-treatment completer: all the randomized participants who permanently discontinue double-blind study drug (or never begin double-blind treatment) and complete some or all of their required study visits/assessments through Visit 22 and have at least one follow-up serum creatinine assessment during Follow-up Period I.
- Non-completer: all the randomized participants who take the study drug (or never take the study drug) but do not complete the Visit 22/ET visit or complete Visit 22/ET visit and do not have at least 1 follow up serum creatinine assessment during Follow-up Period I.

Part 2 completer and non-completer will be defined as the following:

- On-treatment completer: all the randomized participants who enter Part 2 of the study, take open-label study drug in accordance with the protocol through Visit 42 (Week 104), and complete some or all of their required study visits/assessments through Visit 42 and have at least one follow-up serum creatinine assessment during Follow-up Period II.
- Off-treatment completer: all the randomized participants who enter Part 2 of the study, but permanently discontinue open-label study drug (or never begin open-label treatment) and complete some or all of their required study visits/assessments through Visit 42 and have at least one follow-up serum creatinine assessment during Follow-up Period II.
- Non-completer: all the randomized participants who enter Part 2 of the study, take the study drug (or never take the study drug) but do not complete the Visit 42/ET visit or

complete Visit 42/ET visit but do not have at least 1 follow up serum creatinine assessment during Follow-up Period II.

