8.2.1. Sensitivity Analyses of the Primary Efficacy Endpoint

8.2.1.1. Primary Sensitivity Analyses

Sensitivity analyses on the primary efficacy endpoint will be performed using the same ANCOVA model as the primary efficacy analysis with fixed effects for treatment group and the randomization stratification factors (CKD stage [CKD2 versus CKD3/4] and Mayo Clinic ADPKD Image Classification [1C, 1D, or 1E]) and the baseline eGFR as a covariate.

Two sensitivity analyses will be performed on the mITT:

- The annualized change in eGFR (2021 CKD-EPIcr_R) without restriction from baseline to off treatment assessment after Week 52 (mean of 3 eGFR values obtained during off-treatment follow-up visits after Week 52); missing data are handled by multiple imputation:
 - MAR (Section 6.1.4.1.1)
- The annualized change in eGFR (2021 CKD-EPIcr_R) with restriction from baseline to final assessment (mean of 3 eGFR values obtained during Follow-up Period I after Week 52 for on-treatment completers or, for participants who discontinue study drug treatment prior to Visit 22, during the Follow-up Period 8 to 28 days following study drug treatment discontinuation); missing data are handled by multiple imputation:
 - MAR (Section 6.1.4.1.1)
 - MNAR and tipping point analysis (Sections 6.1.4.1.2 & 6.1.4.1.3)

Two sensitivity analyses will be performed on the PEAS:

- The annualized change in off-treatment eGFR (2021 CKD-EPIcr_R) without restriction from baseline to final assessment (mean of 3 eGFR values obtained during Follow-up Period I after Week 52 for on-treatment completers or, for participants who discontinue study drug treatment prior to Visit 22, during the Follow-up Period 8 to 28 days following study drug treatment discontinuation)
- The annualized change in eGFR (2009 CKD-EPI) with restriction from baseline to final assessment (mean of 3 eGFR values obtained during Follow-up Period I after Week 52 for on-treatment completers or, for participants who discontinue study drug treatment prior to Visit 22, during the Follow-up Period 8 to 28 days following study drug treatment discontinuation)

One sensitivity analysis will be performed on the on-treatment completers of the PEAS :

• The annualized change in eGFR (2021 CKD-EPIcr_R) without restriction from baseline to final assessment (mean of 3 eGFR values obtained during Follow-up Period I after Week 52 for on-treatment completers or, for participants who discontinue study drug

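### The protocol's main all-randomised (ITT) sensitivity analysis is assigned in the SAP to an inconsistently defined mITT set, and the switch is not declared

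*SAP*

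**What the plan says.** Protocol 8.4.2 describes the main sensitivity analysis as a comparison of pretreatment eGFR with off-treatment eGFR after the 52-week period, "regardless of adherence to randomized treatment and/or withdrawal for all randomized participants, i.e., Intent-To-Treat participants". Missing Week 52 values are multiply imputed under MAR, and tipping-point analyses of the missing Week 52 data follow in the same paragraph. The protocol synopsis names the same population.

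SAP 8.2.1.1 keeps the Week 52 endpoint and the MAR imputation but changes the population: "Two sensitivity analyses will be performed on the mITT". The second of those two analyses uses a different endpoint. It takes the restricted annualised change to the final assessment, with early follow-up for participants who stop drug, and it carries the tipping-point work.

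SAP 5 contains these statements:

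- ITT: "The ITT includes all participants who were randomized in Part 1".
- mITT: "The mITT includes all participants in the ITT who received at least one dose of study drug in Part 1".
- The Note on the mITT: "Note that the mITT Analysis Set consists of the same set of the participants in the Randomized Safety Set".
- Randomized Safety Set: "The Randomized Safety Set includes all participants who received at least one dose of study drug after randomization".

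SAP 8.1 allows an off-treatment completer to be a randomised participant who did "permanently discontinue double-blind study drug (or never begin double-blind treatment"), provided follow-up creatinine is obtained. Protocol 4.2.1 says the same. In the disposition list of SAP 7.1, treated participants, mITT and Randomized Safety Set share one line, separate from the randomised/ITT line, and completers share a line with the PEAS.

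**The concern.** The protocol's primary and secondary sets already require a dose of randomised drug. The Week 52 ITT analysis is therefore the one place where the protocol checks the result in everyone randomised, whether or not they adhered. If that analysis is limited to participants who started double-blind drug, it no longer does this job.

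The plan expects data from the people concerned. Protocol 6.9 intends all randomised participants to complete every visit. SAP 6.1.4 plans collection from all of them except those who withdraw consent and also refuse any data collection. Observed Week 52 values could thus be collected and then left out. The inconsistent definition also means that two programmers could build different mITT sets from the same SAP.

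**Working it through.** **Which set each analysis uses.** Apart from its definition and its use as the parent of the mITT, the ITT set is named only in the SAP 7.1 disposition list. The efficacy analyses in SAP 8 are assigned to the PEAS, SEAS, PPAS, mITT, on-treatment completers of the PEAS, or P2EAS.

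**Who the mITT contains.**

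1. Definition sentence. SAP 4.1.4.2 treats run-in placebo as study drug: it describes an event that "occurred after the first dose of the study drug (i.e., placebo during the Placebo Run-in Period"). Everyone reaching randomisation has passed through run-in and titration in Part 1. The sentence therefore excludes nobody, and mITT = ITT.
2. Note. The Randomized Safety Set needs a dose after randomisation, so the mITT is the ITT set minus the never-dosed. SAP 7.1 supports this reading by giving treated/mITT a line separate from randomised/ITT.
3. Both cannot hold if anyone is randomised and not dosed. Under the Note, a never-dosed participant can be an off-treatment completer (SAP 8.1) but cannot be in the PEAS, which is built from the mITT. The shared completers/PEAS line in SAP 7.1 is then wrong.

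**Reproducing the plan's sample size.** Inputs from protocol 8.1 and SAP 3.7: difference 1.40, SD 6.20, alpha 0.01, power 90%, allocation 2:1.

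n(placebo) = (1 + 1/2) × (z₀.₉₉₅ + z₀.₉₀)² × SD²/δ² = 1.5 × (2.5758 + 1.2816)² × 38.44/1.96 = 437.7, rounded up to 438.

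Lixivaptan is 2 × 438 = 876, total 1314, which matches the plan. A one-sided test would give 383 placebo and 1149 in total, so the plan's figure is two-sided. At 1350 (450/900) the standard error is 6.20 × √(1/450 + 1/900) = 0.358, and power is Φ(1.40/0.358 − 2.576) = 90.9%.

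**Effect of the population choice.** Let x be the share randomised but never dosed, assumed equal in both arms. The documents give no value, so a range is shown.

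- Kept (ITT): never-dosed lixivaptan participants are assumed to have no drug effect, so the expected difference is 1.40 × (1 − x) with n = 450/900.
- Dropped (mITT under the Note): the expected difference stays 1.40, with n reduced by the factor (1 − x).

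| x | Undosed of 1350 | ITT difference | ITT power | mITT difference | mITT power |
|---|---|---|---|---|---|
| 0 | 0 | 1.400 | 90.91% | 1.40 | 90.91% |
| 0.5% | 6.75 | 1.393 | 90.59% | 1.40 | 90.75% |
| 1% | 13.5 | 1.386 | 90.25% | 1.40 | 90.59% |
| 2% | 27 | 1.372 | 89.56% | 1.40 | 90.25% |
| 5% | 67.5 | 1.330 | 87.28% | 1.40 | 89.18% |

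If non-starting occurred only in the lixivaptan arm, and those participants differed from the rest of their arm by d, dropping them would move the difference by x × d. That is 0.01 × 1.4 = 0.014 at the mild end and 0.05 × 5 = 0.25 at an assumed 5% with d = 5.

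**The case against.** Several points on the other side have force.

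- **The exclusion depends on the reading.** The definition sentence alone drops nobody, so a reader who infers that the SAP simply excludes undosed participants goes too far. This stands. The exclusion comes from the Note and the SAP 7.1 label, and the definition needs repair for that reason.
- **The protocol's own sets exclude the undosed.** A reader might conclude that the SAP removed the randomised population from the primary analysis. It did not. Protocol 8.3 builds the PEAS and SEAS from a Randomized Safety Set that needs a dose of randomised drug. The departure is confined to the sensitivity analysis.
- **Both imputation analyses need not be ITT.** The ITT wording in protocol 8.4.2 belongs to the Week 52 analysis and its tipping-point analyses. It does not describe the SAP's second analysis, with restriction and early follow-up, so that one may stay on the mITT if this is declared.
- **Non-starting should be rare and is unlikely to differ by arm.** Randomisation and dispensing happen at the same visit (protocol 6.3.2), after titration on the same capsule regimen. Participants are not told that this is the randomisation point, and allocation is blinded (protocol 5.3). A large gap between undosed participants in the two arms has no support in the documents, since neither group takes double-blind drug.
- **The SAP may modify the plan.** Protocol 8.14 permits this, and SAP 15 lists the ITT and mITT as added sets. That permission does not remedy a change that is undeclared and rests on a contradictory definition.

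**Conclusion.** The point holds as a mismatch of population between protocol and SAP, together with an inconsistent mITT definition. The protocol's main Week 52 sensitivity analysis is moved from ITT to mITT without a line in SAP 15. Under the Note, no efficacy analysis then uses everyone randomised.

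The likely numerical effect is small: at an assumed 1% undosed, 0.014 mL/min/1.73 m² in the expected difference and about 0.3 percentage points of power. At 5% it is 0.07 and about 1.9 points. These figures assume equal rates in the two arms and no drug effect in the undosed. No stated sample-size figure is wrong. SAP 12 records that five participants were randomised, all terminated early, and that no statistical analyses will be performed, so this concerns the soundness of the plan and not any reported result.

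**What to change.** 1. SAP 8.2.1.1: run the Week 52 MAR analysis, and the Week 52 tipping-point analyses that protocol 8.4.2 describes, on the ITT set as randomised. The imputation model in SAP 6.1.4.1.1 includes treatment duration; state that post-randomisation duration is zero for participants never dosed.
2. SAP 5: give the mITT one definition, namely ITT participants with at least one dose of study drug after randomisation.
3. SAP 7.1: list completers separately from the PEAS.
4. SAP 15: declare any analysis kept on the mITT.

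The cost is SAP wording, a population flag, the duration rule, and programming the tipping-point analyses on the Week 52 endpoint. No additional data collection is needed.
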